3.2.8 Ask a Doctor Before Use Warnings

The “Ask a Doctor” warnings for non-prescription rosuvastatin during the reorder assessment are as follows: kidney disease, drink 3 or more glasses of alcohol daily, taking colchicine, HIV, AIDS or hepatitis medications. Prior to every drug reorder, participants are required to enter the Web App and take an abbreviated medical reorder assessment. If they identify an “Ask a Doctor” warning, they will no longer be able to order drug until they contact a doctor and confirm within the Web App that they can continue to order medicine.

While one of the “Ask a Doctor” warnings could come to the attention of a clinician during the 60- or 120-day touchpoint, following review of the eDiary, or through an unplanned contact from the participant, the clinician will take no action in response to this information. The intent is to determine if participants can identify these warnings within the Web App during the reorder process. This is important because consumers will not have clinicians supporting their decisions when the drug is on the market, and if they do not stop and ask a doctor on their own, it must be demonstrated that they recognize the event and can enter it into the Web App so that the appropriate action can be taken. The information regarding whether a participant contacted a doctor will come from the Targeted Medical and Medication History Form completed by the clinician at Virtual Visit 2. This approach is appropriate in this study because the likelihood of harm to the participant from continuing therapy is very low. Note that Crestor 5 mg is an indicated dose for all of the “Ask a Doctor” situations and participants will not be able to reorder drug unless they indicate the doctor gave them permission to do so.

It is possible that during the 60- or 120-day touchpoint or through an unplanned contact, the participant informs the clinician that they believe they met an “Ask a Doctor” criterion for which they stopped use of the medication and have no intention of restarting mediation. If this occurs, the clinician will make no determination, but will schedule a Virtual Visit 2. At Virtual Visit 2, all procedures will be performed and a final use assessment in the Web App will be conducted for those participants with a previous TASS outcome of “OK to Use” or “Ask a Doctor” and the doctor gave permission to proceed.

If the participant refuses to schedule a Virtual Visit 2, the clinician will attempt to obtain a medical and medication history to determine if the participant did experience an “Ask a Doctor” warning. If the clinician confirms the “Ask a Doctor” warning, the participant will have met the Ask a Doctor endpoints. If not, they have failed the Ask a Doctor endpoints.

See [Appendix B](#) for additional details on how the participant's final use outcome would be assessed based on these different scenarios.

3.2.9 Eligible for Continuous Treatment

Participants eligible for continuous therapy are defined as those with an “OK to Use” outcome or those with an “Ask a Doctor” outcome who indicated the doctor gave them permission to continue treatment, and they continued to have one of these outcomes at all assessments (initial, reorder and final use). Participants who discontinue or withdraw are not eligible for continuous treatment.

3.2.10 Pill Count

At Virtual Visit 2, all administered pill bottles will be returned, and pill count will be assessed. The total number of pills dispensed is based on the number of 45-day or 90-day supplies ordered through the Web App. The number of pills returned is the total number of pills remaining in each of the returned bottles. For those participants who refuse to send back their pill bottles for a final pill count, the option to count the pills with the study personnel via video conference will be given. For those participants who have lost one or more of their pill bottles, the eDiary data will be utilized to reconcile compliance with dosing.

Because there may be instances in which a participant continues study medication when they should not have (i.e., participant experiences “Stop Use,” “Do Not Use,” or “Ask a Doctor” warning) but does not stop medication, in order to properly assess compliance with continuous dosing, the intended duration of treatment will be used rather than the actual duration of treatment. The intended duration of treatment is as follows:

Intended Duration of Treatment =	(Intended Treatment Stop Date – Date Participant Received First Supply of Study Drug) + 1 Day
----------------------------------	---

where the date of intended treatment stop will be the date when the medication was intended to be stopped (i.e., the date of “Stop Use” warning, the date of the “Do Not Use” warning, the date of the “Ask a Doctor” warning in situations where the participant did not confirm the doctor gave them permission to use the drug, the date of discontinuation or withdrawal, or for participants who did not receive one of the previous outcomes, the date of Visit 2).

Data listings will be provided for participants TASS initial study drug order and their overall study drug accountability.

3.2.11 eDiary

The eDiary will be used to gather minimal and unbiased data on the participant's use of the IP. The information to be gathered will include dosing (date/time and amount of IP taken), adverse

events (changes in health), and medication changes. The participant will record the unique ID from the study drug bottle to confirm receipt of the product.

At the 60-day and 120-day planned telephone contacts, the eDiary will be reviewed to determine if “Stop Use” criteria may be present and to ask about any changes in health.

In assessing supply period compliance, the total number of pills dispensed in supply period i will be either 45 or 90 based on the supply ordered and the total number of pills taken is determined based on the information recorded in the eDiary. The start date for assessing compliance in the eDiary will be the first day that the participant records taking the medication. From the start date, supply periods for evaluation of the eDiary are calculated based on the supply ordered. Therefore, the first supply period will include next 45 days for a 45-day supply and the next 90 days for a 90-day supply. The next supply period will start immediately after the first supply period ends, and the duration is based on supply. This method for determining the dates in the eDiary that are assessed for dosing relative to the supply periods will continue until the subject completes Virtual Visit 2 or has an event for which early stopping of therapy is required. In other words, the duration of treatment in the supply period for evaluation in the eDiary can be less than 45 or 90 days in those situations where the participant experiences an event that requires stopping therapy. Thus, the intended duration of treatment for supply period i will be calculated as follows:

Intended Duration of Treatment in Supply Period i =	(Intended Treatment Stop Date in Supply Period i – Date Participant Received First Supply of Study Drug in Supply Period i) + 1 Day
--	--

where the date of intended treatment stop in supply period i will be the date when the entire supply of medication was intended to be used by the participant (assuming one tablet is taken per day) or when the medication was intended to be stopped (i.e., the end date of intended supply period based on number of pills ordered, the date of “Stop Use” warning, the date of “Do Not Use” warning, the date of discontinuation or withdrawal).

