 - All participants at Virtual Visit 1 will be allowed to enter the use period of the study provided a CMOG clinician has not determined that the participant has a condition for which treatment would pose an unacceptable risk (e.g., allergy to rosuvastatin or a woman who is breastfeeding or pregnant).

Use Period

- 16 The use period of the study begins on the day that the product is delivered to the address provided by the participant. The use period lasts 6-months. During this period, participants have the option to purchase more product.
- 17 Participants will need to utilize the eDiary to record the unique bottle ID(s) received for this initial shipment and any subsequent reorder shipments received to confirm receipt of delivery of the study drug.

- 18 Participants will be instructed to use the eDiary to record when they took study drug, have changes to any medications and have any changes in health status. The diary will be reviewed for AEs by a CMOG clinician at the day 60 and day 120 phone call (phone calls described in Step 22 below) and at the Virtual Visit 2. AEs will be followed to resolution. See Section 8.1 for further details regarding eDiary.
- 19 The timing for reordering drug for a 45-day order and a 90-day order will be after 5 days from the date of last delivery. Emails will also be used to inform participants when they should reorder. They will receive a reorder email at day 25 for a 45-day supply order and at day 45 for a 90-day supply order. Participants will have a TASS assessment performed during the reorder. Provided they receive an “OK to Use” outcome or an “Ask a Doctor” outcome and indicate the doctor gave them permission to continue treatment, they can reorder. However, the participant does not interact with a CMOG clinician to have their medical and medication history assessed during reorders.

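### SAP 3.2.11 counts tablets in back-to-back eDiary windows but starts each denominator at receipt of the supply and omits Visit 2 as an end date, so a shortened period with perfect dosing can score below 50%

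*SAP*

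**What the plan says.** **Tablets counted.** SAP 3.2.11 starts the eDiary count on the first day a dose is recorded and sets the first window at 45 or 90 days, according to the supply ordered. After that, "The next supply period will start immediately after the first supply period ends, and the duration is based on supply". Windows of this kind are laid end to end "until the subject completes Virtual Visit 2 or has an event for which early stopping of therapy is required".

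**Denominator.** The formula in the same section is stop date minus start date plus one day. The start date is the "Date Participant Received First Supply of Study Drug in Supply Period" i. The stop date is described in two ways. One places it at the point "when the entire supply of medication was intended to be used by the participant (assuming one tablet is taken per day"). The other, in the list that follows, is "the end date of intended supply period based on number of pills ordered". The rest of that list is the Stop Use date, the Do Not Use date, and discontinuation or withdrawal.

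**The parallel list.** SAP 3.2.10 defines intended duration for the pill-count endpoint. Its list has two further entries. The first concerns Ask a Doctor and covers a "warning in situations where the participant did not confirm the doctor gave them permission to use the drug". The second is a catch-all: "for participants who did not receive one of the previous outcomes, the date of Visit 2".

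**Pass rule.** SAP 4.2.3 calls a participant longitudinally compliant only if every supply period lies between 50% and 120%. The target is a point estimate of at least 50% of participants.

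**Reordering.** Under Protocol 8, Step 19, the time for a reorder "will be after 5 days from the date of last delivery". The reminder email goes out at day 25 for a 45-day supply and at day 45 for a 90-day supply.

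**The concern.** The numerator and the denominator of one ratio cover different days. A supply reordered when prompted arrives weeks before the previous window closes. The denominator for period 2 can then include days on which the participant was still using supply 1, and the tablets taken on those days have already been credited to period 1. A full-length period may or may not be distorted, depending on how the stop date is read. A period cut short by a stop event is distorted on either reading of the stop date.

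Separately, the text ends the windows at Visit 2 but the stop-date list does not. A participant whose last window has just opened at Visit 2 can therefore be scored over a full supply.

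Because every period must pass, one such artefact turns a fully adherent participant into a failure on a secondary endpoint with a stated target.

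**Working it through.** **Assumptions.** One tablet every day from delivery. Delivery of supply 1 is Day 1 (Protocol 8, Step 15; the Schedule of Activities prints Day 0). The reorder is placed when the email is sent. The documents give no shipping time, so 0 to 10 days is shown.

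**Intended figure.** With a full 45-day window 2 (days 46-90) and a denominator that starts with the window, the score is 45/(90 - 46 + 1) = 45/45 = 100%.

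**1. Period 2 cut short by a stop event on day E, supply 2 delivered on day d.**

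- 45-day supplies: score = (E - 45)/(E - d + 1), which is below 50% when E < 91 - d.
- 90-day supplies: score = (E - 90)/(E - d + 1), which is below 50% when E < 181 - d.
- Example: d = 26, E = 60 gives 15/35 = 42.9%.

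| Supply | Shipping (days) | d | Stop-event days that fail |
|---|---|---|---|
| 45-day | 0 | 26 | 46-64 |
| 45-day | 5 | 31 | 46-59 |
| 45-day | 10 | 36 | 46-54 |
| 90-day | 0 | 46 | 91-134 |
| 90-day | 5 | 51 | 91-129 |
| 90-day | 10 | 56 | 91-124 |

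In all these ranges E is no later than d + 44 (or d + 89). It therefore does not matter whether the supply is taken to end 45 or 90 days after delivery or at the window end. Counting the email day the other way (d = 25) gives 15/36 = 41.7% for the example and moves the limits by at most one day.

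**2. Window cut short by Visit 2.** Protocol 1.3 gives Day 180 a window of -7/+14 days, so Visit 2 can fall as late as day 194. After 180 days of dosing, a participant holding a further supply has 1 to 14 days in a new window:

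- 45-day supply: 1/45 = 2.2% to 14/45 = 31.1%.
- 90-day supply: 1/90 = 1.1% to 14/90 = 15.6%.

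These use the shortest possible denominator. A denominator running from an early delivery to the window end would be longer. Orders of 45, 90 and 90 with Visit 2 on day 173 give 38/90 = 42.2%, even with the denominator started at the window.

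**3. Full-length periods.** If the stop date is counted from delivery, every full period is 45 or 90 days and scores 100%. If it is the window end:

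- Second 90-day period: 90/(180 - 46 + 1) = 90/135 = 66.7% with zero shipping time, a pass.
- Fourth 45-day period: deliveries on days 1, 26, 51 and 76 give 45/(180 - 76 + 1) = 45/105 = 42.9%, a fail. With 5 days' shipping the fourth delivery is on day 91, and 45/90 = 50.0% just passes.

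**4. After the fix.** The example in step 1 becomes 15/(60 - 46 + 1) = 15/15 = 100%, and the longest case in step 2 becomes 14/14 = 100%.

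**The case against.** The best defence is that SAP 3.2.11 presents its formula as a consequence of the windows it has just described, so a sensible programmer would start period i with its window and stop at Visit 2. That may well be the intent, and Visit 2 does appear in the text. But the formula names receipt of the supply, and the list of end dates, given as complete, lacks Visit 2. Followed as written, it gives the results above.

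Three objections stand in part:

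- The denominator of the longitudinal rate is limited to per-protocol participants whose compliance was assessed in every supply period. This could be read to drop participants with a truncated period instead of failing them. The SAP does not say so.
- The effect is confined to early stoppers, holders of surplus supply and, on the window-end reading, late 45-day periods. Protocol 3.1 expects warning events to be infrequent, and withdrawals are outside the per-protocol set. Participants who discontinue with sufficient data are inside it.
- For early reorderers the error lowers the rate, so it works against the 50% target.

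A reader might also infer that the pill-count endpoint is affected, because SAP 4.2.3 fills missing bottles from the eDiary. The documents do not support this: the eDiary supplies only the number of tablets taken, and the denominator comes from 3.2.10.

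**Conclusion.** The inconsistency is real and should be corrected. Perfect dosing can score 42.9% in a period ended by a stop event, and at most 31.1% or 15.6% in a window just opened before Visit 2. Unless truncated participants are dropped, one such period makes the participant non-compliant. The figures rest on reordering at the email date and on assumed shipping times. How many participants are affected cannot be worked out, because order mix and shipping times are not given. The endpoint is secondary and has a point-estimate target with no test.

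It would be too strong to infer that adherent participants generally fail, since ordinary two-by-90-day completers pass on either reading of the stop date.

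It would also be too strong to call the 50% persistence threshold wrong. Protocol 3.1 justifies it by about 44% of people still refilling at 180 days, while the endpoint divides by those eligible for continuous treatment, which excludes anyone who discontinues or withdraws (SAP 3.2.9). If about 500 of 1,000 entrants were eligible, 50% of them would be 250/1,000 = 25% of entrants. But the eligible count is not given and the base of the 44% is not stated. That the two rates are not comparable is a possibility and has not been shown.

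**What to change.** In SAP 3.2.11:

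- Start each supply-period denominator on the first day of its eDiary window: the first recorded dose for period 1, and the day after the previous window ends for later periods.
- End it at the earliest of window end, listed stop date or Visit 2.
- Reconcile the stop-date lists of 3.2.10 and 3.2.11, including the unresolved Ask a Doctor date.
- In 4.2.3, state whether truncated periods count in the longitudinal rate.

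The cost is SAP wording and one changed derivation. Scores of shortened periods rise for early reorderers and can fall for late ones.

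As a secondary suggestion, keep the persistence endpoint and its threshold but label it as persistence among those eligible for continuous treatment. State the base of the 44%, and rest any comparison with it on a supportive rate that has all AUS ITT participants as denominator. That adds one table, and the supportive rate will be lower than the endpoint if, as planned, many participants are lost during use.

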3.3 Safety Variables

3.3.1 Adverse Events

Adverse Events will be collected from the time of signature of ICF, throughout the use period and up until 30 days after study drug completion or discontinuation. AEs will be collected and documented during the treatment and 30-day follow-up periods. All AEs will be followed to resolution. Serious AEs (SAEs) will be recorded from the time of signing of informed consent form.

A treatment-period AE are those AEs with an onset date on or after drug delivery date or worsening of pre-existing AEs on or after the drug delivery date.

An SAE is an AE occurring during any study phase that fulfils one or more of the following criteria:

- Results in death
- Is immediately life-threatening
- Requires in-participant hospitalization or prolongation of existing hospitalization
- Results in persistent or significant disability or incapacity
- Is a congenital abnormality or birth defect
- Is an important medical event that may jeopardize the participant or may require medical treatment to prevent one of the outcomes listed above.

Prior to analysis, all AEs will be coded using the latest version of the MedDRA coding dictionary.

3.3.2 Reporting of AEs/SAEs in Relation to COVID-19

All AEs/SAEs should be reported in line with instructions for safety reporting documented in the CSP. For patients experiencing signs and symptoms indicating an infection, an attempt will be made to determine whether the COVID-19 virus is the infectious organism, and the AE will be recorded accordingly. If a patient presents with clinical signs and symptoms suggestive of COVID-19, a test will be requested where possible:

If the test is positive, record “COVID-19 positive” in the Adverse Event Field.

If the test is negative, record “COVID-19 negative” in the Adverse Event Field, along with the AE/SAE signs and symptoms and/or other diagnosis.

If a test was not performed or the test was negative, but the signs and symptoms, as judged by the Investigator, are suggestive of COVID-19 infection, record “COVID-19 suspected” in the Adverse Event Field. If the investigator has other concurrent diagnoses for the patient’s signs and symptoms (eg, pneumonia), these will be recorded as separate AEs.

4 ANALYSIS METHODS

4.1 General Principles

4.1.1 Types of Analyses

Analyses will consist of descriptive statistics (n, mean, standard deviation, median, minimum, maximum, and Quartiles 1 and 3 (Q1 and Q3)) for all continuous variables. Frequency counts and percentages will be summarized for all categorical variables. Two-sided 95% confidence intervals will also be provided for the co-primary endpoints, unless otherwise stated.

4.1.2 Subgroup Analyses

Results for all endpoints will be summarized by literacy group (limited, normal) as assessed by the REALM test as well as by sex at birth, race and age group (less than 50 years old, 50 – 65 years old, >65 years old) gathered from the CMOG responses in the Targeted Medical and Medication History Form at Visit 1. Results will also be assessed relative to Order Preference (based on the participant’s study drug order quantity, 45- or 90- day supply from the Order History dataset).

4.1.3 Missing Data Conventions

All primary analyses, except the first co-primary endpoint, will be conducted based on a complete case analysis (i.e., observed data).

4.1.3.1 Missing Dates

In some instances, a participant’s medical portal may only reflect the month and year a diagnostic test was conducted. While this information is sufficient to assess whether a diagnostic test was conducted within the required time frame according to the study, any dates with a missing day for a diagnostic test will be imputed using the following:

Missing Date	Imputation
Missing day (ex. March 2020)	The missing day will be imputed as the first day of the month.

For the exploratory efficacy analyses where time (in days) to compliance with a “Stop Use”, “Do Not Use” or “Ask a Doctor” warning is assessed, handling of missing dates will be done in accordance with the scenarios shown in [Appendix F](#).

4.1.3.2 Missing Data Imputation

The primary analysis of the first co-primary endpoint will be based on a worst case scenario missing data imputation where all participants in the respective analysis population with a missing CMOG initial TASS outcome will be counted as Incorrect for the endpoint. In addition to the worst case scenario analysis for the first co-primary endpoint, sensitivity analyses will be performed on the participants in the SS population with a non-missing initial TASS outcome for the (Sensitivity Analysis #1) CMOG (i.e., complete case analysis) and with missing Overall Correct Initial TASS Outcome data imputed using alternative methods for use in a sensitivity analysis. For those participants in the SS population, missing data imputation methods for this endpoint are as follows:

1. Best Case Scenario: All missing data assumed to be a success for the Overall Correct Initial TASS Outcome (i.e., participants who did not complete the targeted medical and medication history at the Virtual Visit 1, and, therefore, have a missing initial TASS outcome for the CMOG will be treated as Correct for the Overall Correct Initial TASS

Outcome) (Sensitivity Analysis #2).

2. Tipping Point Analysis: Missing data will be imputed to identify the largest number of missing cases that could be incorrect and still yield statistically significant results, had the outcome of all missing cases been observed. The proportion of Overall Correct Initial TASS Outcome along with 95% exact confidence intervals will be calculated. The estimated proportions and corresponding 95% confidence intervals will be displayed graphically as a function of the number of assumed Overall Correct Initial TASS outcome among participants with missing data on the x-axis. The success threshold of 85% will be displayed as a horizontal line in the graph. (Sensitivity Analysis #2).

In addition to the complete case analysis for the second co-primary endpoint, missing data for the Overall Correct Final Use Outcome will be imputed for use in sensitivity analyses. For those participants in the AUS ITT population, missing data imputation methods for this endpoint are as follows:

1. Best Case Scenario: All missing data assumed to be a success for the Overall Correct Final Use Outcome (i.e., participants who did not complete Virtual Visit 2 or did not provide sufficient medical history to make a final use assessment, and, therefore, have a missing final use outcome for the CMOG will be treated as Correct for the Overall Correct Final Use Outcome) (Sensitivity Analysis #1).
2. Worst Case Scenario: All missing data assumed to be a failure for the Overall Correct Final Use Outcome (i.e., participants who did not complete Virtual Visit 2 or did not provide sufficient medical history to make a final use assessment, and, therefore, have a missing final use outcome for the CMOG will be treated as Incorrect for the Overall Correct Final Use Outcome) (Sensitivity Analysis #1).
3. Tipping Point Analysis: Missing data will be imputed to identify the largest number of missing cases that could be incorrect and still yield statistically significant results, had an outcome for all missing cases been observed (Sensitivity Analysis #1).

For the third co-primary endpoint, participants in the primary LDL-C efficacy population (AUS ITT) with missing verified on-treatment LDL-C values, missing data will be imputed using various missing data imputation methods. The missing data imputation methods are as follows:

1. Best Case Scenario: All participants with missing LDL-C reduction due to missing verified LDL-C values will be treated as having a 40% reduction in LDL-C from baseline to Visit 2 (i.e., PCFB = -40%) (Sensitivity Analysis #2).
2. Worst Case Scenario: All participants with missing LDL-C reduction due to missing verified LDL-C values will be treated as having no reduction in LDL-C from baseline to Visit 2 (i.e., PCFB = 0%) (Sensitivity Analysis #2).

3. Tipping Point Analysis: Missing LDL-C reduction data due to missing verified LDL-C values will be imputed over the range of 0% reduction to 40% reduction (i.e., assuming that all participants with missing data had the same reduction in LDL-C ranging from 0% to 40%) and point estimates and corresponding 95% confidence intervals will be displayed graphically as a function of the assumed reduction in LDL-C. The graph will include a horizontal line corresponding to the success threshold of a 15% reduction (Sensitivity Analysis #2).

